Study Treatment	
IMCnyeso will be supplied as a sterile, frozen solution, in individual, single-use glass vials at a concentration of 0.5 mg/mL.
 
IMCnyeso will be administered via weekly (QW) intravenous (IV) infusions. For each patient, the first dose will be infused over 2 hours (\pm15 minutes); for dose levels \leq 30 mcg; the first dose infusion time may be reduced to 1 hour (\pm10 minutes). If the first dose is well tolerated without \geq Grade 2 infusion and/or a hypersensitivity reaction, a given patient's subsequent infusion times may be reduced to 1 hour (\pm10 minutes) starting

	
at C1D8, and further reduced to 30 minutes (\pm10 minutes) starting at C3D1 provided the above conditions continue to be met.
 
For all study medication administration, a physician must be present at the site, or immediately available to respond to emergencies. Patients will be hospitalized for 2 nights following administration of the first dose (C1D1) of IMCnyeso and will remain at the site for overnight observation following the second dose (C1D8). After reviewing safety, PK, and cytokine data from at least 3 patients enrolled at a given dose level, the SST may decide that 1 night of hospitalization is adequate after the first dose for subsequent patients (with longer hospitalization if indicated). During Phase I, patients receiving IPE over three doses will be hospitalized overnight after each of the first three doses (C1D1, C1D8, and C1D15). The SST may decide to reduce the minimum required monitoring time during Phase II to no less than 8 hours post-end of infusion for C1D1, C1D8, and/or C1D15. Fully functional resuscitation equipment and medications to handle acute infusion-related emergencies (eg, anaphylaxis, cytokine release syndrome [CRS]) must be available at each study site.

Population Under Study	In Phase I, HLA-A*02:01-positive patients with a diagnosis of NY-ESO-1 and/or LAGE-1A positive advanced NSCLC, melanoma, urothelial carcinoma, or synovial sarcoma will be enrolled. In Phase II, patients with HLA-A*02:01 positive and NY-ESO-1 and/or LAGE-1A positive advanced NSCLC, urothelial carcinoma, or synovial sarcoma will be enrolled and treated at the RP2D. Patients must meet all eligibility criteria to commence dosing.
Efficacy Assessments	Tumor response will be determined locally according to RECIST v.1.1. During the study, Immunocore may decide to have a central review of the radiological assessments performed.

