6.2 Treatment Regimen and In-Patient Hospitalization

Patients enrolled in this study will receive treatment with single-agent IMCnyeso dosed weekly on Days 1, 8, 15, and 22 of each 4-week cycle. All dosages prescribed and dispensed to patients and all dose changes during the study must be recorded on the Dosage Administration Record and electronic case report form (eCRF).

For each administration of study medication, a physician must be present at the site or immediately available to respond to emergencies. Study sites will be instructed on the conservative management of symptoms associated with CRS (eg, hypotension), as described in [Section 6.15](#). Fully functional resuscitation equipment and medications to handle acute infusion-related emergencies (eg, anaphylaxis, CRS) must be available at each study site.

Patients will be hospitalized for 2 nights following the administration of the first dose (C1D1) of IMCnyeso and will remain at the site for overnight observation following administration of the second dose (C1D8). In addition, patients receiving intra-patient escalation (IPE) will be hospitalized overnight following the first three doses (C1D1, C1D8, and C1D15). After reviewing safety, PK, and cytokine data from at least 3 patients enrolled at a given dose level, the SST may decide that 1 night of hospitalization is adequate after the first dose for subsequent

patients (with longer hospitalization if indicated). After Phase I is completed and the SST has reviewed all available relevant data for at least 6 patients at the RP2D, the SST may decide to reduce the minimum required monitoring time during the Phase II portion of the study to no less than 8 hours post-end of infusion on C1D1, C1D8, and/or C1D15 (with longer hospitalization if clinically indicated). Patients who experience certain AEs may require additional in-patient monitoring as described in [Section 6.15](#).

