13.4 Schedule of Cycle 1 Assessments, Intra-Patient Escalation Regimen

Patients who receive IPE should follow the schedule below during Cycle 1, and the main schedule at all other times, including Pre-Screening, Screening, Cycle 2 and subsequent treatment cycles, and Follow-up.

The Cycle 1 schedule is provided in [Table 13-13](#). Assessments marked “X” should be performed prior to dosing. Assessments that are to be performed at multiple timepoints are marked with the number of timepoints (including optional timepoints, if applicable) for the visit (eg, 2× is twice) and details of the timepoints are provided in the footnote. Additional details regarding the assessments are provided in [Section 7.4](#).

Table 13-13: Schedule of Cycle 1 Assessments, IPE Regimen

Procedure	Cycle 1						
Day of Cycle	1	2	8	9	15	16	22
Adverse events	X	X	X	X	X	X	X
Concomitant medications	X	X	X	X	X	X	X
Safety Assessments							
Complete physical examination	X						
Abbreviated physical examination			X		X		X
Weight	X						
Vital signs		~14×		~14×		~14×	3×
12-lead ECG (single)	2×						
ECOG performance status	X						
Hematology panel	X	X	X	X	X		X
Chemistry panel	X		X		X		X
Thyroid function	X						
Urine pregnancy test (women of childbearing potential)	X						
PK and Immunogenicity Assessments							
Pharmacokinetic sampling	3×	X	8×	X	8×	X	3×
Immunogenicity sampling	X		X		X		
[REDACTED]		Between C1D9 and C1D16 (required for ≥ 10 patients in Phase II, optional for all other patients)					
[REDACTED]							

Procedure	Cycle 1					
IMCnyeso Administration						
One-step IPE	C1D1 dose level		Target dose level		Target dose level	Target dose level
Two-step IPE	C1D1 dose level		C1D8 level		Target dose level	Target dose level

AE = adverse event; C#D# = Cycle # Day #; CRS = cytokine release syndrome; [REDACTED]; ECG = electrocardiogram; ECOG = Eastern Cooperative Oncology Group; EOI = end of infusion; hr = hour(s); min = minutes; [REDACTED] PK = pharmacokinetics; [REDACTED]

ECG assessments are to be done pre-dose and within 1 hour of EOI on indicated days.

Vitals (body temperature, pulse, respiratory rate, blood pressure; oxygen saturation should also be assessed for \geq first 3 cycles of treatment), are to be assessed at the following timepoints:

- C1D1/C1D2, C1D8/C1D9, and C1D15/C1D16: pre-dose (within 2 hours), EOI (within 15 min), every 2 hours (\pm 15 min) through 8-hour post-EOI, then every 4 hours (\pm 30 min) until discharge

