3.3 Treatments

For this study, the terms investigational drug and study medication refer to IMCnyeso.

Patients enrolled in this study will receive treatment with single agent IMCnyeso, dosed weekly on Days 1, 8, 15 and 22 until disease progression or other reason to discontinue. Patients will be hospitalized for 2 nights following the administration of the first dose (C1D1) of IMCnyeso and

will remain at the site for overnight observation following administration of the second dose (C1D8). In addition, patients receiving intra-patient escalation (IPE) will be hospitalized overnight following the first three doses (C1D1, C1D8, and C1D15). After reviewing safety, PK, and cytokine data from at least 3 patients enrolled at a given dose level, the SST may decide that one night of hospitalization is adequate after the first dose for subsequent patients (with longer hospitalization if indicated). After Phase I is completed and the SST would review all available relevant data for at least 6 patients at the RP2D, the SST may decide to reduce the minimum required monitoring time during the Phase II portion of the study to no less than 8 hours post-end of infusion on C1D1, C1D8, and/or C1D15 (with longer hospitalization if clinically indicated). Patients who experience certain AEs may require additional in-patient monitoring as described in Section 6.15 of Protocol V4.0.

For each patient, the first dose will be infused over 2 hours (± 15 minutes); for dose levels ≤ 30 mcg; the first dose may be infused over 1 hour (± 10 minutes). If the first dose is well tolerated without \geq Grade 2 infusion and/or a hypersensitivity reaction, a given patient's subsequent infusion times may be reduced to 1 hour (± 10 minutes) starting at C1D8, and further reduced to 30 minutes (± 10 minutes) starting at C3D1 provided the above conditions continue to be met. Investigators may prolong the infusion time for individual patients if medically indicated at any time.

Cohorts 1- 4 would be fixed dose and cohorts 5 - 7 will introduce an intra-patient escalation (IPE). If the severity of cytokine-mediated AEs tend to become less severe following the initial doses of study drug using a fixed-dose regimen, the SST may initiate a step 1 IPE regimen, in which a lower dose is given on Cycle 1 Day 1 and a higher (target) dose is given on Cycle 1 Day 8 and beyond (for details: Section 6.10.1 of the Protocol V4.0).

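### The Synopsis and Section 6.2 disagree on which intra-patient escalation (IPE) patients must stay overnight after the third dose (C1D15)

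*Protocol*

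**What the plan says.** **Synopsis, Study Treatment.** Every patient stays two nights after C1D1, which the SST may later cut to one, and "will remain at the site for overnight observation following the second dose (C1D8"). For IPE the text then adds: "During Phase I, patients receiving IPE over three doses will be hospitalized overnight after each of the first three doses". The next sentence reads "The SST may decide to reduce the minimum required monitoring time during Phase II to no less than 8 hours post-end of infusion", and it names C1D15 among the days to which this may apply.

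**Protocol Section 6.2.** The same general stays apply after C1D1 and C1D8. The IPE sentence is "In addition, patients receiving intra-patient escalation (IPE) will be hospitalized overnight following the first three doses", with C1D1, C1D8 and C1D15 listed. It mentions neither phase nor number of steps. Once Phase I is complete and data on at least 6 patients at the RP2D have been reviewed, "the SST may decide to reduce the minimum required monitoring time during the Phase II portion of the study", again with C1D15 among the days.

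**SAP Section 3.3.** This repeats Section 6.2: "patients receiving intra-patient escalation (IPE) will be hospitalized overnight following the first three doses".

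**Protocol Section 13.4, Table 13-13.** One Cycle 1 schedule serves all IPE patients, with separate dosing rows for one-step and two-step. Vital signs follow the same intensive plan on all three day pairs, "C1D1/C1D2, C1D8/C1D9, and C1D15/C1D16: pre-dose (within 2 hours), EOI (within 15 min), every 2 hours", continuing until discharge.

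**The concern.** The Synopsis narrows the C1D15 stay in two ways that the other texts do not: to Phase I, and to IPE over three doses. A site working from the Synopsis has no required C1D15 night for a 1-step patient, or for any Phase II IPE patient. A site working from Section 6.2 has one.

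This is a monitoring rule in a first-in-human study of a CD3 bispecific, with cytokine release syndrome (CRS) as an adverse event of special interest. In a 2-step regimen C1D15 is the first dose at the target level. Section 1.4 reports that with the related molecule tebentafusp symptoms typically came 4 to 24 hours after the first two or three doses, and it expects a similar CRS risk here. Patients on the same regimen could be watched differently after that dose depending on which section a site follows, and a missing C1D15 night could not be classed consistently as a protocol deviation.

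**Working it through.** No sample size, power or error rate is involved, so the check sets the texts side by side and then counts patients.

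**Step 1: what IPE over three doses means.** The term is not defined. Under Section 6.10.1 a 1-step regimen reaches its target on C1D8, the second dose. A 2-step regimen has an intermediate dose on C1D8 and its target from C1D15, the third dose. The Synopsis phrase therefore fits 2-step IPE.

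**Step 2: which nights differ.** C1D1 and C1D8 do not, because the Synopsis, Section 6.2 and SAP 3.3 all require those stays for every patient. Only C1D15 is left.

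**Step 3: the C1D15 overnight stay by regimen and phase.**

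| Phase | Regimen | Synopsis | Section 6.2 and SAP 3.3 | Result |
|---|---|---|---|---|
| I | Fixed dose | Not stated | Not stated | Agree |
| I | 1-step | Not stated | Required | Conflict |
| I | 2-step | Required | Required | Agree |
| II | Fixed dose | Not stated | Not stated | Agree |
| II | 1-step | Not stated | Required unless the SST reduces it | Conflict |
| II | 2-step | Not stated | Required unless the SST reduces it | Conflict |

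Three of the four IPE situations conflict.

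**Step 4: does another section settle it?**
- Table 13-13 leans towards Section 6.2. For both IPE regimens it has about 14 vital-sign timepoints over C1D15/C1D16, and 24-hour PK and cytokine samples on C1D16. The fixed-dose schedule (Table 7-2) has three vital-sign timepoints on C1D15 and no Day 16 visit.
- The Synopsis is inconsistent with itself. Its Phase II reduction option names C1D15, although it sets no C1D15 stay in Phase II that could be reduced.
- Section 7.4.5 describes sampling at C1D15 as out-patient without setting IPE patients apart, which adds to the ambiguity.

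**Step 5: how many patients.** Section 6.10.1 allows either IPE regimen into Phase II. Section 3.2 gives three cohorts of up to 9 patients, each expandable to 24.
- Initial enrollment: 3 x 9 = 27 at most.
- Full expansion: 3 x 24 = 72 at most.
- If the RP2D is a fixed dose, or the SST shortens C1D15 monitoring before the first Phase II patient is dosed: 0.

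In Phase I the conflict concerns 1-step IPE. SAP Table 1 has one such cohort, cohort 5 (30-100 mcg, n = 5), and lists it among the dose levels already tested.

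**The case against.** The strongest reply is that the Synopsis omits these patients but does not exempt them. It never says that the stay applies only to the group it names. A site that follows Section 6.2, the dedicated section on hospitalization, satisfies both texts. SAP 3.3 and Table 13-13 point the same way, and the Synopsis's own reduction option presupposes C1D15 monitoring in Phase II. On this view one summary sentence is loosely worded and no competing rule exists.

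That is a fair account of how the text may have arisen, and it limits the seriousness of the point. It does not remove the conflict, because a site reading the Synopsis finds no required C1D15 night for a 1-step patient or for any Phase II IPE patient. That holds even before the SST review on which Section 6.2 makes any reduction depend.

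A reader might infer more, and four such inferences fail:
- **That the stays after all three doses differ.** They do not; see Step 2.
- **That Section 6.2 contradicts itself on C1D1**, with two nights in one sentence and an overnight stay in the IPE sentence. The IPE sentence is introduced as an addition, and two nights include an overnight stay, so the sentences are compatible.
- **That Phase I and Phase II safety data at the RP2D would not be comparable.** This is not shown. Table 13-13 requires adverse events, vital signs, PK and cytokines over C1D15/C1D16 for every IPE patient. Section 6.2 openly allows shorter monitoring in Phase II. The rationale for Global Amendment 3 also states that CRS signs with IMCnyeso had so far appeared within a few hours of dosing.
- **That cohort 5 patients missed a stay.** Nothing in the documents says so, and new wording cannot change stays already completed.

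**Conclusion.** The point holds as an internal inconsistency in a current monitoring rule. It is confined to the C1D15 night, for 1-step IPE in Phase I and for either IPE regimen in Phase II until the SST uses its option for that day.

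Its forward reach is Phase II. The figure of 27 assumes that the RP2D uses an IPE regimen, that all three cohorts open and fill their first stage, and that the SST has not shortened C1D15 monitoring. The figure of 72 also needs at least one response among the first 9 patients in each cohort and a sponsor decision to expand each one fully. It is a ceiling and should not be read as an expected number.

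The supportable consequence is uneven observation after C1D15 between sites on the same regimen. The finding also rests on reading the undefined Synopsis phrase as 2-step IPE. On a wider reading that takes in 1-step IPE, the Phase I conflict would disappear and the Phase II conflict would remain. The matter should be settled before Phase II patients are dosed on an IPE regimen.

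**What to change.** Reconcile the Synopsis sentence with Section 6.2, SAP 3.3 and Table 13-13. One statement should give the required C1D15 stay for each regimen (fixed, 1-step, 2-step) in each phase, and every section should repeat it or refer to it. Either define IPE over three doses or replace it with the Section 6.10.1 terms. Make the Synopsis's Phase II reduction option match whatever C1D15 requirement is stated, and have Section 7.4.5 distinguish IPE patients when it describes C1D15 sampling. Which stay is required is a clinical decision for the sponsor, and this review takes no position on it.

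The cost is amendment wording. No analysis, sample size or data collection needs to change on statistical grounds.

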1 BACKGROUND

1.1 Overview of IMCnyeso

Immunocore is developing a new biological entity, IMCnyeso, for the treatment of advanced cancers that are positive for the cancer-testis antigens New York esophageal squamous cell carcinoma-1 (NY-ESO-1) and/or L antigen family member-1 isoform A (LAGE-1A). IMCnyeso is an immune mobilizing T cell receptor against cancer (ImmTAC), a bispecific protein therapeutic comprising a soluble, affinity-enhanced T cell receptor (TCR) fused to an antibody single-chain variable fragment (scFv). One other investigational ImmTAC drug, tebentafusp (IMCgp100), is currently in development and being tested in patients with metastatic melanoma (Middleton, 2016).

1.2 Mechanism of Action of IMCnyeso

IMCnyeso is a 77 kilodalton (kDa) protein which is manufactured in *Escherichia coli*. Affinity and binding half-life data were generated using soluble proteins and surface plasmon resonance (BIAcore) methods, as shown in Figure 1-1.

[figure not shown]

Figure 1-1: IMCnyeso Structure and Functional Domains

Anti-CD3 = anti-cluster of differentiation 3; K_D = dissociation constant; LAGE-1A = L antigen family member-1 isoform A; NY-ESO-1 = New York esophageal squamous cell cancer-1; $T_{1/2}$ = half-life; TCR = T cell receptor.

The targeting portion of IMCnyeso (the soluble TCR) binds to a peptide fragment of the NY-ESO-1 or LAGE-1A tumor antigen presented by human leukocyte antigen (HLA)-A*02:01 on the surface of cancer cells (Liddy, 2012). HLA molecules are polymorphic; the HLA-A*02:01 allele is expressed by approximately 40% to 50% of the Caucasian population in the Western World (<http://www.allelefrequencies.net/>). The scFv effector end can bind to CD3 on any T cell, redirecting the T cell to produce effector cytokines and/or kill the cell presenting the target (see [Figure 1-2](#)). In addition, IMCnyeso-mediated tumor lysis may prime an endogenous anti-tumor immune response.

[figure not shown]

Figure 1-2: Schematic Representation of IMCnyeso Mechanism of Action

CD3 = cluster of differentiation 3; HLA = human leukocyte antigen; LAGE-1A = L antigen family member-1 isoform A; NY-ESO-1 = New York esophageal squamous cell carcinoma-1.

1.2.1 New York Esophageal Squamous Cell Carcinoma-1 and L Antigen Family Member-1 Isoform A

The peptide recognized by IMCnyeso is found in NY-ESO-1 and LAGE-1A ([Figure 1-3](#)). In contrast, a related tumor antigen, L antigen family member-1 isoform B (LAGE-1B) does not contain the specific peptide recognized by IMCnyeso molecule.

[figure not shown]

Figure 1-3: Comparison of NY-ESO-1, LAGE-1A, LAGE-1B Protein, and Peptide Expression

LAGE-1A = L antigen family member-1 isoform A; LAGE-1B = L antigen family member-1 isoform B; NY-ESO-1 = New York esophageal squamous cell carcinoma-1.

Expression of NY-ESO-1 and LAGE-1A is restricted to cell types related to human testis and human cancers. The testis is not susceptible to systemic T cell responses and is considered immune-privileged (Zhao, 2014). NY-ESO-1 and LAGE-1A are aberrantly expressed in a wide range of cancer indications at varying frequencies (Nicholaou, 2006; National Cancer Institute, 2017). For these reasons, NY-ESO-1 / LAGE-1A is an attractive target in cancer immunotherapy.

1.3 Non-Clinical Experience with IMCnyeso

The hypothesis of the IMCnyeso preclinical and clinical development programs is that tumors with high expression of the NY-ESO and/or LAGE-1A antigen would be most sensitive to the mechanism of action of IMCnyeso: T cell redirection against cells presenting the HLA-A*02:01-restricted NY-ESO-1 / LAGE-1A peptide.

The soluble TCR targeting end of IMCnyeso is highly specific for human NY-ESO-1 / LAGE-1A peptide presented by human HLA-A*02:01 and does not bind to peptide/HLA complexes from non-human species. The anti-CD3 effector end of IMCnyeso is specific for human CD3 and does not bind to or activate T cells from other species. Therefore, there is no relevant species in which IMCnyeso pharmacology or toxicology can be tested, and the relevance of non-human pharmacokinetic (PK) studies are considered limited.

1.3.1 Non-Clinical Pharmacology of IMCnyeso

IMCnyeso was evaluated in a series of in vitro investigations to assess potential anti-tumor activity in patients with tumors that express NY-ESO-1 and/or LAGE-1A. These data can be summarized as follows:

- IMCnyeso could redirect T cell activity to tumor cells that express NY-ESO-1 and/or LAGE-1A.
- In vitro, IMCnyeso potently recruits and activates healthy donor and cancer patient peripheral blood mononuclear cells (PBMCs), leading to the release of pro-inflammatory cytokines, chemokines, and killing of cancer cell targets. The fullest extent of redirected T cell killing can take up to 72 hours.
- In vitro, IMCnyeso potently recruits and activates CD3-positive T cells including CD8-positive and CD4-positive T cells resulting in cancer-cell killing, polyfunctional T cell activation, and proliferation and expansion of T cells.
- T cell activation occurs from 5 picomolar (pM) IMCnyeso and the induction of target-cell killing from 10 pM. Above this concentration, tumor cell killing increases in a dose-dependent fashion, reaching a plateau at 1 nanomolar (nM). These assays were used to determine the minimum anticipated biological effect level (MABEL) and the starting dose for this study (see [Section 6.9](#)).

These data demonstrate that IMCnyeso is a potent tumor-killing agent. Therefore, an investigation into the effects of the drug in patients with tumors expressing NY-ESO-1 and/or LAGE-1A is warranted.

1.3.2 IMCnyeso Single-Agent Pharmacokinetics

Preclinical PK studies allow determination of parameters including the maximum observed concentration (C_{max}), the time of maximum concentration (T_{max}) to C_{max} , the mean residence time, half-life in the plasma, and clearance. Together, these PK data can be modelled to form a basis for predictions of how the drug may be dealt with by the human body. When examined alongside distribution and excretion studies these models may provide insight into the fate of IMCnyeso following administration.

A single-dose, intravenous (IV) PK study was conducted in C57BL/6 mice. Nine mice were flat dosed (0.1 mg/kg) followed by micro-sampling over 24 hours (Report GSK01-IMC076). Data indicate a C_{max} 1.33 mcg/mL, and a $t_{1/2}$ of approximately 2 hours.

